9.1 Descriptive analysis

Using data pooled across all sites, the study sample will be characterized based on demographic and clinical variables measured at randomization, unless otherwise indicated. Specifically, the following variables will be described:

1. Age (years)
2. Sex (male, female, undifferentiated, no response)
3. Race (Black/African American, White/Caucasian, American Indian/Alaskan Native, Asian, Native Hawaiian/Other Pacific Islander, other, no answer)
4. Ethnicity (Hispanic, non-Hispanic)
5. Race/ethnicity (non-Hispanic Black/African American, non-Hispanic White/Caucasian, Hispanic, other)
6. Body mass index (kg/m²)
7. Presence of comorbidities (yes/no):
 - a. chronic cardiac disease
 - b. chronic pulmonary disease
 - c. chronic kidney disease
 - d. chronic liver disease
 - e. chronic neurological disease
 - f. malignant neoplasm
 - g. chronic hematologic disease
 - h. AIDS/HIV
 - i. obesity
 - j. diabetes with complications
 - k. diabetes without complications
 - l. rheumatologic disorder
 - m. malnutrition
 - n. immunosuppressive conditions
8. Tobacco product use (current, former, never)
9. E-cigarette or vaping product use (current, former, never)
10. Chronic use of medication (yes/no):
 - a. ACE inhibitors
 - b. angiotensin receptor blockers
11. Receipt of azithromycin in the past week
12. Presence of symptoms (yes/no):
 - a. Cough
 - b. Fever
 - c. Shortness of breath
 - d. Chest pain
 - e. Abdominal pain

- f. Nausea
- g. Diarrhea
- h. Body aches
- i. Weakness/fatigue

13. Total number of symptoms reported (count)

14. Symptom duration (days)

9.2 Subject disposition

The number of participants completing each stage of the trial will be summarized with frequencies and percentages to describe the number screened, the number randomized, the number reaching target data collection times by arm at Study Day 8, Study Day 15 (primary), and Study Day 29 for collection of the primary ordinal outcome status, and the number that dropped out by arm and the accompanying reason where known (e.g., death, toxicity, withdrew consent). A CONSORT diagram will be generated (Schulz et al. 2010).

9.3 Derived variables

This study involves several derived variables, such as body mass index and the seven-level ordinal outcome scale. During the data collection process, each component of the derived variable is collected and the first stage in data analysis will be to generate and validate the derived variable. Depending on the distribution of the seven-category modified COVID-19 ordinal outcomes scale, certain categories may need to be combined based upon few or no events.

The primary outcome through Study Day 15 will be derived primarily through the daily surveys (from Days 1 to 16 post-randomization) and supplemented by the Study Day 29 Chart Review to verify details about hospitalization or other healthcare encounters recorded. The method for derivation of other variables not described will be clearly articulated in the analysis report if needed.

9.4 Treatment compliance, protocol deviations and protocol violations

Major protocol deviations and violations will be described. Adherence to the schedule for taking study medications will be reported. Major protocol deviations that will be reported are failure of participant to adhere to the study medication schedule, errors in shipping and handling of study medication including shipping the incorrect medication, and other protocol deviations deemed by the study executive committee to affect the overall integrity of the data. Any such determination will be made before unblinding to treatment arm.

10 Efficacy Analyses

All continuous and categorical variables will be summarized as described previously. The analytic approach is Bayesian with results presented as credible intervals and posterior probabilities for specific hypotheses as defined in the following sections unless otherwise noted.

10.1 Primary Efficacy Analysis

The primary outcome of the Modified COVID Ordinal Outcomes Scale from Study Day 1 through Study Day 15 will be evaluated in the ITT dataset using a Bayesian longitudinal proportional odds model. The model will include a random intercept for each participant to account for the repeated measurements over time to calculate the posterior probability that a treatment arm compared to the placebo-controlled arm has an $OR > 1$, suggesting any benefit for the treatment. The proportional odds assumption will be examined using graphical methods—e. g., the logit of the empirical cumulative distribution function of the ordinal scale should be parallel among categories of

covariates. If proportionality is clearly violated, we will consider partial proportional odds or non-proportional odds models.

The model will be adjusted for the variables described in Section 8.3. To account for changes in the effect size between treatment groups from Study Day 1 to Study Day 15, an interaction between randomized group and time will be included. Time will initially be modeled using a cubic spline, but it may be modified to a simpler or more complex representation of time if needed to appropriately model the effect over time.

The prior for the intercept for the proportional odds regression model will assume a Dirichlet distribution. The treatment effect, as defined as a log odds ratio in the model, will have a normal prior defined so that $P(OR > 1) = P(OR < 1) = 0.5$ (i.e., equally as harmful as beneficial) and $P(OR > 2) = P(OR < \frac{1}{2}) = 0.025$ (i.e., large effects in either direction unlikely), with the variance computed to satisfy these criteria. For all other covariates the prior distributions will be normal with mean 0 and a larger variance to reflect the uncertainty of their potential effect.

The convergence of the Markov chain Monte Carlo simulations will be checked via diagnostics, with alternative priors, models, and chain lengths/burn-ins explored if necessary to achieve convergence and satisfy any model assumptions.

10.1.1 Secondary Analyses of Primary Efficacy Endpoint

We will replicate the primary analyses using the per protocol dataset and the safety dataset.

10.2 Secondary Efficacy Analyses

10.2.1 Analyses of Secondary Endpoints

For time-to-event outcomes we will utilize survival models (e.g., Cox proportional hazards models), and dichotomized outcomes will be evaluated using logistic regression. The continuous outcomes such as hospital free days are penalized for death and so an ordinal model will be fit in preference to using linear regression. Secondary endpoint models will be fit using normal priors with mean 0 and larger variance to reflect the uncertainty of their potential effect on all regression coefficients, with convergence evaluated similarly to the primary endpoint.

10.3 Subgroup analyses

The currently recommended approach to subgroup analysis is to prespecify subgroups where there is a clear biological rationale, and otherwise not to create subgroups unless the data indicate differential treatment effects based on potential subgrouping variables. Given how little is known about COVID-19 and possible treatment response, we will examine the potential of differential treatment effects in key subgroups of interest based upon previous definitions unless otherwise noted:

- Age
- Sex
- Race/ethnicity
- BMI
- Baseline renal function defined as known severe chronic kidney disease requiring dialysis, kidney disease not requiring dialysis, no known history of kidney disease
- Hypertension
- Diabetes defined as diabetes with complications, diabetes without complications, not diabetic

- Cardiovascular disease
- Duration of respiratory symptoms prior to randomization

Interactions will not be tested together within the same model but will be tested one by one. Potentially significant subgroups will be identified by evaluating the posterior weight assigned to a model with and without the interaction by Bayesian stacking. If the model including the interaction has a posterior weight of 80% or greater, we will proceed with fitting the model within subgroups. For continuous variables, graphical methods will be used to show how the treatment effect changes over the range of the continuous variable.

11 Safety Analyses

The safety analysis set will be used for safety analyses. Summary statistics will be calculated as described in Section 9. When calculating the incidence of adverse events, or any sub-classification thereof by treatment, time period, severity, etc., each subject will only be counted once for a given safety outcome and any repetitions will be reported separately; the denominator will be the total safety population size.

Three tables summarizing adverse events will be created:

- All-Cause Mortality: A table of all anticipated and unanticipated deaths due to any cause, with number and frequency of such events in each arm/group of the clinical study.
- Serious Adverse Events: A table of all anticipated and unanticipated serious adverse events, grouped by organ system, with number and frequency of such events in each arm/group of the clinical study.
- Other (Not Including Serious) Adverse Events: A table of anticipated and unanticipated events (not included in the serious adverse event table) that exceed a frequency threshold of 5% within any arm of the clinical study, grouped by organ system, with number and frequency of such events in each arm/group of the clinical study.

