## 7. STATISTICAL CONSIDERATIONS

Using intention-to-treat principles, we will compare the primary outcome (Modified COVID Ordinal Outcomes Scale score to Day 15) between patients in each intervention group and the control group using a proportional odds model, adjusted for the following co-variables: age, gender, and duration of acute respiratory infection symptoms prior to randomization. The proportional odds assumption will mainly be examined using graphical methods—e. g., the logit of the empirical cumulative distribution function of the ordinal scale should be parallel among categories of covariates. If proportionality is clearly violated, we will consider partial proportional odds or non-proportional odds models.

With type I error of 0.05, enrolling 540 patients in the primary population will provide 90% power to detect an odds ratio of 1.75. Accounting for a ~10% loss to follow-up rate, we will plan to enroll **600 patients**. This sample size and power assumes a frequentist analysis, which is generally more conservative than what is needed for a Bayesian approach. We will plan an initial DSMB evaluation of safety and feasibility after n=100 patients have been enrolled; efficacy will not be considered at these analyses. The trial will then have frequent interim analyses with details on specifics on timing of meetings, as well as efficacy and futility stopping rules to be detailed in the Statistical Analysis Plan, to be finalized prior to the first interim analyses.

Additional analyses will include comparisons of secondary outcomes between treatment groups. We will compare the Modified COVID Ordinal Outcome Scale daily over the 14-day intervention period using a recently developed longitudinal proportional odds model that can incorporate the information on intermediate states between baseline and Study Day 15. For time-to-event outcomes we will utilize survival models (e.g., Cox proportional hazards models), continuous outcomes will utilize linear regression, and dichotomized outcomes will be evaluated using logistic regression. We will also evaluate primary and main secondary outcomes in key subgroups of interest. *A priori* subgroups for analysis will include age, sex, race/ethnicity, facility residence, BMI, baseline renal function, hypertension, diabetes, cardiovascular disease, and duration of respiratory symptoms.

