6.4 Timing of study procedures and outcomes assessments

The day of randomization is defined as Baseline and the receipt of the study drug is defined as “Study Day 1”. It is possible for it to take up to two days for study medications to arrive at a participant’s home. For the purposes of analysis, Study Day 1 will be counted as the day on which study medications are received by the participant. To ensure symptoms are assessed daily while on study, and to ensure the primary outcome can be measured through Study Day 15, symptoms are collected daily from the day following randomization to sixteen days following randomization. The symptoms assessed on Study Day 1 (day of receipt of medication) to Study Day 15 are included in the measurements for this trial. At Study Day 15, the primary outcome is assessed. At Study Day 29, additional outcomes are assessed.

7 Sample Size

This study is designed to be analyzed using a Bayesian approach, accepting the possibility of adaptations or sample size adjustments as the trial progresses. Although the design as detailed is Bayesian in nature, a frequentist sample size and target power are provided for consistency with FDA guidance and recommendations. To provide a sample size estimate, we calculated a sample size of 540 patients equally distributed among study arms is needed to have 90% power to detect an odds ratio of 1.75 or greater assuming a traditional proportional odds model and a type I error of 0.05, as proposed by Whitehead (1993). Accounting for an approximate 10% loss to follow-up rate, we plan to enroll 600 patients

An example of the difference between study arms resulting in such an odds ratio is shown in the table. This is based on recommendations from the World Health Organization for COVID-19 Master Protocols that were in place at the time this study was designed

Category	Placebo Arm Proportion	Treatment Arm Proportion
1-Death	1%	0.6%
2-Hospitalized on mechanical ventilation or ECMO	3%	1.8%
3-Hospitalized on supplemental oxygen	4%	2.4%
4-Hospitalized not on supplemental oxygen	3%	1.9%
5-Not hospitalized with symptoms and limitation in activity	10%	6.6%
6-Not hospitalized with symptoms but with no limitation in activity	24%	18.7%
7-Not hospitalized without symptoms nor limitation in activity	55%	68.1%

8 General Analysis Considerations

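### Within-subgroup effects are fitted only after an 80% stacking-weight filter, which overstates small and moderate interactions on average, and the SAP does not commit to reporting factors that fail it

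*SAP*

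**What the plan says.** SAP section 10.3 lists nine factors: age, sex, race/ethnicity, BMI, baseline renal function, hypertension, diabetes, cardiovascular disease and symptom duration. "Interactions will not be tested together within the same model but will be tested one by one." Each is judged by "evaluating the posterior weight assigned to a model with and without the interaction by Bayesian stacking", followed by the gate: "If the model including the interaction has a posterior weight of 80% or greater, we will proceed with fitting the model within subgroups." The stated reason is restraint: the recommended approach is to pre-specify subgroups that have a biological rationale, and "otherwise not to create subgroups unless the data indicate differential treatment effects based on potential subgrouping variables". A separate sentence covers the continuous factors: "For continuous variables, graphical methods will be used to show how the treatment effect changes over the range of the continuous variable." It does not say whether these graphs depend on the weight.

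The section does not say that interaction estimates or weights will be reported for all nine factors, nor that they will be withheld. It plans no correction for the selection and states no prior for the interaction term.

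Protocol section 7 mentions no filter: "We will also evaluate primary and main secondary outcomes in key subgroups of interest." Its list has ten factors. The extra one is facility residence, which the SAP does not carry.

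**The concern.** A result that is shown only when it looks large will look larger, on average, than it is. Here the within-subgroup fit depends on the interaction having already reached a set strength in the same data, and nothing in the plan offsets that. A reader who sees a subgroup result could take a modest or absent difference for a substantial one. A reader who sees none could not judge how consistent the effect is across the pre-specified groups unless the authors chose to show more than the SAP requires.

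The separate refits add a lesser problem. SAP section 8.3 lists eight adjustment covariates and a center random intercept. Section 10.1 adds a participant random intercept and a treatment-by-time interaction. Estimating all of this again inside each subgroup gives up shared information, although the interaction model already yields effects by subgroup.

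**Working it through.** **Inputs from the documents.** SAP section 7 says that "540 patients equally distributed among study arms is needed to have 90% power to detect an odds ratio of 1.75 or greater", with a type I error of 0.05 and the Whitehead formula. Its table gives the category proportions. SAP section 10.1 gives the treatment prior, with P(OR > 2) = 0.025. SAP section 10.3 gives the filter.

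**Assumptions not in the documents.** Two-level subgroups with a share of 20% to 50%; Day 15 information only; a flat prior on the interaction unless stated.

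**1. Reproduce the plan's figure.** N = 12(z₁ + z₂)² / [θ²(1 − Σp̄³)], where p̄ is the mean of the two table columns.
- 1 − Σp̄³ = 0.7565, and θ = ln 1.75 = 0.5596.
- Two-sided: 12 × (1.960 + 1.282)² / (0.5596² × 0.7565) = 532, within 2% of the stated 540. One-sided gives 434, which does not match.
- 540 / 0.9 = 600, as planned.

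**2. Precision of an interaction.** SE of the main log OR = √[12 / (540 × 0.7565)] = 0.171. For a subgroup share q, the interaction SE = 0.171 × √[1/q + 1/(1 − q)]. This is 0.343, 0.374 and 0.428 for shares of 50%, 30% and 20%.

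**3. What 80% weight requires.** I approximate the two-model weight as 1 − k/T, with T the likelihood-ratio chi-square on k degrees of freedom. Then 0.80 means T ≥ 5k. The chance of passing with no interaction is 0.025, 0.0067 and 0.0018 for 1, 2 and 3 df. For 1 df the cut is |z| = √5 = 2.24. Simulating leave-one-out stacking directly, with a Gaussian stand-in and 4,000 trials per setting, gave a smallest passing |z| of 1.8 to 2.2 and a null pass rate of 2.4% to 2.9%. The two agree closely.

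With equal subgroups the cut is 2.24 × 0.343 = 0.77 on the log scale, or a ratio of ORs of about 2.15. Under a flat prior, any ratio that passes is therefore at least that far from 1.

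**4. What passing estimates look like.** Equal subgroups, SE 0.343. The average is the exponential of the mean absolute log ratio among those passing. For the skeptical column, the prior SD is ln 2 / 1.96 = 0.354 and the SE within a half-sample is 0.171 × √2 = 0.242. The shrinkage factor is 0.354² / (0.354² + 0.242²) = 0.68.

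| True ratio of ORs | Passes | Average, flat prior | Average, skeptical prior within subgroups |
|---|---|---|---|
| 1.00 | 2.5% | 2.4 | 1.8 |
| 1.25 | 6% | 2.5 | 1.9 |
| 1.40 | 11% | 2.5 | 1.9 |
| 1.75 | 27% | 2.7 | 1.9 |
| 2.00 | 42% | 2.8 | 2.0 |
| 3.00 | 83% | 3.3 | 2.3 |

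The stacking simulation, with a flat prior and shares of 50% to 20%, put the exaggeration of the log ratio at 3.7 to 4.4 times for a true 1.25, 2.3 to 2.8 times for 1.5, 1.5 to 1.7 times for 2.0, 1.09 to 1.23 times for 3.0 and 1.02 to 1.09 times for 4.0.

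**5. At least one false pass among the factors, if independent.**
- Six categorical factors: four with 1 df (sex taken as two levels; renal function has two because exclusion criterion 10 removes dialysis patients), diabetes with 2 df and race/ethnicity with 3 df. 1 − (0.9747⁴ × 0.9933 × 0.9982) = 10.5%.
- All nine gated and treated as two-level, at the simulated 2.9%: 1 − 0.971⁹ = 23%.

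**6. Effect of reporting everything.** In the simulation with equal subgroups and no true interaction, the mean absolute log ratio is 0.27 over all trials (a ratio of 1.3) and 0.89 among those passing (a ratio of 2.4).

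**The case against.** The gate is deliberate. It keeps the report from filling with subgroup contrasts that the trial was not sized to estimate, and a forest plot of everything carries its own risk of over-reading. The consequence is also limited: the primary analysis, sample size and stopping rules are untouched. All of that stands, and it is why this is a minor point. But a gate on observed strength picks out the results most inflated by chance. Restraint is better served by showing all factors with their intervals and weights.

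Three stronger readings are tempting, and the documents support none of them.
- A reader might infer that every subgroup effect shown is exaggerated. The bias is an average one. With a flat prior it nearly vanishes at a true ratio of 4, and at a true ratio of 3 some 20% to 40% of selected estimates lie below the truth. If the skeptical treatment prior is used within subgroups, it is gone by a ratio of about 2.0.
- A reader might infer that the other factors go unreported. The SAP is silent on this. The interaction model is fitted for every factor, and the graphs for age, BMI and symptom duration are not expressly tied to the weight.
- A reader might see a flat contradiction with the protocol. Protocol section 7 does not promise an estimate in every subgroup, and fitting and weighing an interaction model is a form of evaluation. What remains is that one document states a filter, the other does not, and their lists differ.

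**Conclusion.** The point holds as a cheap improvement. Section 10.3 conditions within-subgroup fits on the strength of the observed interaction and does not commit to reporting the factors that fail. For absent, small or moderate interactions the effects so selected are overstated on average. In the illustration, a true ratio of ORs of 1.40 is shown about one time in nine, and then as roughly 2.5 with a flat prior or 1.9 with the skeptical one.

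These sizes rest on two equal subgroups, Day 15 information at n=540, and an approximation to the stacking weight that simulation supports. A more precise longitudinal model, or a shrinking prior on the interaction, would reduce them. The false-pass range of roughly 10% to 23% also depends on how many factors are gated and on independence between them. The direction of the bias depends on none of these choices as long as the true interaction is not large.

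**What to change.** In SAP section 10.3:
- Report the treatment OR with its credible interval for each level of every categorical factor, taken from the interaction models already fitted.
- Show the effect curve for each continuous factor whatever its weight.
- Give the stacking weight beside each result as a descriptor instead of a gate, and drop the separate within-subgroup refits.
- State the prior for the interaction term, and label the whole set exploratory.
- Reconcile the section with Protocol section 7, both on the filter and on facility residence.

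The cost is one forest plot and a few curves from models that must be run anyway, with no new data. The downside is that wide intervals will be on display, so the text needs a caution against over-reading any single one.

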11.1 Adverse Events, Serious Adverse Events, and other Events

The summary statistics will be produced in accordance with section 9. Adverse events, serious adverse events, and other events are defined in Appendix C of the study protocol. The discontinuation of study medication due to potential adverse events or side effects will be summarized by self-reported termination of study treatment and reported adverse events or side effects.

12 Reporting Conventions

For the purposes of the statistical analysis plan report, posterior probabilities and p-values ≥ 0.001 will be reported to 3 decimal places; values less than 0.001 will be reported as “ <0.001 ”. The mean, standard deviation, and any other statistics other than quantiles, will be reported to one decimal place greater than the original data. Quantiles, such as median, or minimum and maximum will use the same number of decimal places as the original data. Estimated parameters, not on the same scale as raw observations (e.g. regression coefficients) will be reported to 3 decimal places.

13 References

Crainiceanu CM and Crainiceanu A. The upstrap. *Biostatistics* 21.2 (2020): e164-e166.

Harrell F. rmsb: Bayesian Regression Modeling Strategies. R package version 0.0.1. (2020): <https://CRAN.R-project.org/package=rmsb>

Whitehead J. Sample size calculations for ordered categorical data. *Statistics in medicine* 12.24 (1993): 2257-2271.
